1. Physiotherapy techniques are an effective element of pain control in the postoperative chest surgery patient.
2. The quality of life of postoperative chest surgery patients improves with the application of analgesic physiotherapy techniques.
3. Respiratory parameters improve in a shorter time if pain control is carried out during respiratory physiotherapy sessions.
4. As a result, the healthcare expenditure involved in caring for these patients decreases considerably.

The objectives of this work are therefore defined as follows:

Objective one: To demonstrate that physical pain control using transcutaneous electrostimulation (TENS) results in effective physiotherapy for the improvement of respiratory capacities.

Objective two: To demonstrate that improvement in respiratory capacity improves patients' quality of life.

Objective three: To demonstrate that effective physiotherapy results in less time spent in outpatient care, leading to a reduction in the case-mix of rehabilitation and a reduction in the health care costs associated with this intervention.

HYPOTHESIS

Physical pain control using transcutaneous electrostimulation (TENS) in patients who have undergone chest surgery allows effective physiotherapy that improves respiratory capacity and quality of life and reduces health care costs.

MATERIAL AND METHOD

DEFINITION OF THE STUDY

This is a prospective, randomised study in which the aim is to study the value of an analgesic technique (TENS). The study will be carried out on patients undergoing thoracic surgery for pleural, pulmonary or mediastinal procedures of varying complexity. Patients will be recruited once the immediate postoperative period has passed, with a deadline of 7 days after the operation for inclusion in the study. There will be three groups of patients:

Group 1.- Patients treated with anterior, lateral or axillary thoracotomy.

Group 2.- Patients treated with videothoracoscopy with three or more entry doors and/or with mini-thoracotomy assistance.

Group 3.- Patients treated with videothoracoscopy with one or two entry doors.

Inclusion criteria

Patients treated with each of the interventions described and who are between 18 and 80 years of age.

Signed informed consent to participate in the study. Exclusion

criteria

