Once the patient has undergone surgery, the data corresponding to the surgical intervention performed will be collected. Once the period of 7 days has elapsed after the operation and in the absence of complications and pleural drainage, the period of respiratory physiotherapy will begin.

QUALITY OF LIFE ASSESSMENT

The health questionnaire SF-36 (Short Form Health Survey) will be used. This questionnaire is used in medical research, mental health research and health-related research in general. It provides an overview of a person's state of health, with the advantage that it is easy and quick to fill in and simple to evaluate. Similarly, by allowing numerical assessment of different aspects of a person's health, it can be used to assess the health status of the individual.

The questionnaire is an excellent tool for any health-related research. It contains 36 questions that address different aspects related to the daily life of the person filling in the questionnaire. These questions are grouped and measured in 8 sections that are assessed independently and give rise to 8 dimensions measured by the questionnaire.

The eight dimensions are:

1. Physical functioning.
2. Limitation due to physical problems.
3. Body pain.
4. Functioning or social role.
5. Mental health.
6. Limitation due to emotional problems.
7. Vitality energy or fatigue.
8. General perception of health. (Annex 1).

In 1991, the International Quality of Life Assessment Project (IQOLA) was initiated, consisting mainly of adapting and testing the cross-cultural applicability of a generic instrument called the Short Form 36 Health Survey (SF-36) (27).

The Spanish version of the SF-36 is one of the most widely used generic instruments in Spain, both in descriptive studies that measure the impact on HRQOL in different patient populations and for the evaluation of therapeutic interventions (28).

PAIN ASSESSMENT

The tools necessary to make a correct assessment of pain. In this sense, two ways of measuring pain will be established:

1. Self-reports, where the visual analogue scale (VAS) will be the basic measurement tool. Pain will be marked on a scale from 0 (no pain) to 10 (maximum possible pain).
2. The standardised tests, as an objective of the study, also aim to analyse sensory, affective and behavioural aspects of pain in these patients, which is why the Mc Gill test will be the tool to be taken into account (Appendix 2).

ASSESSMENT OF RESPIRATORY FUNCTION

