[name] [name]. Tasks: carrying out interventions, data collection, participation in the production of publications and presentations.

[name] [name]. Tasks: carrying out interventions, data collection.

[name] [name]. Tasks: assessment and design of respiratory tests, participation in publications and presentations.

[name] [name]. Tasks: assessment and design of respiratory tests, participation in publications and presentations.

[name] [name]. Tasks: participation in the design of the work, data collection and participation in the production of publications and presentations.

WORK PLAN

1. Patient recruitment and study of patients: January 2015 to December 2017.

2. Collection of data to complement the Clinical History.

Step 3. Introduction to the study. Explanation of the procedure. Signed consent form.

Step 4. Measurement of parameters:

1. Measurement of pain, Mc Gill test.
2. Measurement of respiratory parameters. Spirometry.
3. Quality of Life Measure. SF-36.
4. Measured with the Minnesota Multiphasic Personality Inventory.
5. Counting days of treatment.

Step 5. Start of the respiratory physiotherapy programme. It will be carried out in the respiratory physiotherapy unit of the University Hospital of Gran Canaria [name]. Patients will be divided into the two groups described above and will be included in the treatment programme. The sequence for the intervention group will be as follows:

1. Explanation of the programme.
2. Placement of external analgesic measures (TENS). The frequency of application would be 100 hz as this is the type of application that produces the greatest analgesia.
10,11,12,13
3. Implementation of the treatment regimen, for x days.
4. In the middle of the programme, measurement of all the above

parameters. Step 6. Continuation of the physiotherapy programme.

Step 7. Completion of the physiotherapy programme. Measurement of all parameters again, plus accounting of treatment days.

In the control group, the same would be done but no intensity would be given when applying TENS. The steps to follow would be the same.

ECONOMIC STUDY

Within the economic study that will define this work, we will highlight two fundamental points:

Portable spirometer brand..... 1500 Euros.

Publication of results..... 1500 Euros.

Attendance at Conferences and Scientific Conferences 750 Euros.

Publication in scientific journals in the sector..... 750 Euros.

TOTAL 3000 Euros.

BIBLIOGRAPHY

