5. Does your current health limit your ability to **pick up or carry your shopping bag**?
1 Yes, it limits me a lot 2

Yes, it limits me

somewhat

3 No, it does not limit me at all

6. Does your current health limit your ability to **climb several flights of stairs**? 1 Yes, it limits me a lot.

2 Yes, it limits me a little

bit 3 No, it does not limit

me at all

7. Does your current health limit your ability to **climb a single flight of stairs**? 1 Yes, it limits me a lot.

2 Yes, it limits me a little

bit 3 No, it does not limit

me at all

8. Does your current health limit you from **bending or kneeling**?
1 Yes, it limits me a lot 2

Yes, it limits me

somewhat

3 No, it does not limit me at all

9. Does your current health limit you to walk **a kilometre or more**? 1 Yes, it limits me a lot

2 Yes, it limits me a bit 3

No, it does not limit me at

all

10. Does your current health limit you to walk **several blocks** (several hundred metres)? 1
Yes, it limits me a lot

2 Yes, it limits me a bit 3

No, it does not limit me at

all

11. Does your current health limit you to walk **only one block** (about 100 metres)? 1 Yes, it limits me a lot

2 Yes, it limits me a bit 3

No, it does not limit me at

all

12. Does your current health limit your ability to **bathe or dress yourself?**

1 Yes, it limits me a lot 2

Yes, it limits me

somewhat

3 No, it does not limit me at all

THE FOLLOWING QUESTIONS REFER TO PROBLEMS IN YOUR WORK OR DAILY ACTIVITIES.

13. During the last 4 weeks, did you have to **reduce the time you** spent at work or on your daily activities because of your physical health? 1
1 Yes

2 No

14. During the last 4 weeks, did you do **less** than you would have liked to do, because of your physical health? 1 Yes
1 Yes

2 No

15. During the last 4 weeks, did you have to **give up any tasks** at work or in your daily activities because of your physical health? 1 Yes

2 No

16. During the last 4 weeks, did you have **difficulty** in doing your work or daily activities (e.g., did it cost you more than usual), because of your physical health?

1 Yes

2 No

17. During the last 4 weeks, did you have to **reduce the time you** spent at work or in your daily activities because of an emotional problem?

(like being sad, depressed, or nervous?)

1 Yes

2 No

18. During the last 4 weeks, did you do **less** than you would have liked to do, because of any emotional problems (such as being sad, depressed, or nervous)?

1 Yes

2 No

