19. During the last 4 weeks, did you not do your work or daily activities as **carefully** as usual, because of some problem

emotional (such as being sad, depressed, or nervous?)

1 Yes

2 No

20.- During the last 4 weeks, to what extent have your physical health or emotional problems hindered your usual social activities with family, friends, neighbours or other people?

Not at all

A little

Regular

Quite a lot

Very much

21. 21.- Did you have **pain** in any part of your body during the last 4 weeks?

1 No, not at all 2

Yes, very little 3

Yes, a little bit

4 Yes, moderate 5

Yes, very much

6 Yes, very much so

22. During the last 4 weeks, to what extent has the pain made it difficult for you to do your usual work (including work outside the home and housework)?

1 Nothing

2 Somewhat

3 Regular

4 Quite

5 A lot

THE FOLLOWING QUESTIONS ARE ABOUT HOW YOU HAVE BEEN FEELING AND HOW THINGS HAVE BEEN GOING FOR YOU OVER THE LAST 4 WEEKS. FOR EACH QUESTION, PLEASE ANSWER THE QUESTION THAT MOST CLOSELY RESEMBLES HOW YOU HAVE BEEN FEELING.

23. During the last 4 weeks, how much of the time did you feel full of **vitality**?

1 Always

2 Almost always 3

Often 4 Sometimes

5 Only ever 6

Never

24. 23.- During the last 4 weeks, how much time were you very **nervous**?

1 Always

2 Almost always 3

Many times 4

Sometimes

5 Only ever 6 Never

25. During the last 4 weeks, for how long did you feel so **low in morale** that nothing could cheer you up?

1 Always

2 Almost always 3

Often 4 Sometimes

5 Only some of the time

6 Never

26. During the last 4 weeks, how much of the time did you feel **calm and peaceful**? 1 Always

2 Almost always 3

Often 4 Sometimes

5 Only ever 6 Never

27. During the last 4 weeks, how much of the time did you have a **lot of energy**? 1 Always

2 Almost always 3

Often 4 Sometimes

5 Only ever 6 Never

28. During the last 4 weeks, how much of the time did you feel **discouraged and sad**? 1 Always

2 Almost always 3

Often 4 Sometimes

5 Only ever 6 Never

29. During the last 4 weeks, for how long have you felt **exhausted**? 1 Always

2 Almost always 3

Often 4 Sometimes

5 Only ever 6 Never

30. During the last 4 weeks, how long did you feel **happy**? 1 Always

2 Almost always 3

Often 4 Sometimes

5 Only some of the time

6 Never

31. During the last 4 weeks, for how long did you feel **tired**? 1 Always

2 Almost always 3

Often 4 Sometimes

5 Only ever 6 Never

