32. During the last 4 weeks, how often has physical health or emotional problems made it difficult for you to carry out social activities (such as visiting

friends or family)?

1 Always

2 Almost always 3

Sometimes

4 Only ever 5 Never

PLEASE SAY WHETHER YOU THINK EACH OF THE FOLLOWING STATEMENTS IS TRUE OR FALSE.

33. I think I get sick more easily than other people. 1 Absolutely true

2 Fairly certain 3

Don't know

4 Quite false

5 Completely false

34. I am as healthy as anyone else.

1 Absolutely true 2

Quite true

3 I don't know

4 Quite false

5 Completely false

35. I think my health is going to get worse.

1 Absolutely true 2

Quite true

3 I don't know

4 Quite false

5 Completely false

36. My health is excellent.
1 Absolutely true 2

Quite true

3 I don't know

4 Quite false

5 Completely false

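### The first SF-36 is completed about a week after surgery but recalls four weeks, so change from it in vitality, mental health and one social-function item cannot be read as postoperative recovery

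*Protocol*

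**What the plan says.** Annex 1 reproduces the questionnaire in full.

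- The four-week window begins at item 13 ("During the last 4 weeks, did you have to"), includes the bodily pain items ("in any part of your body during the last 4 weeks") and the feelings items from 23 on, which are headed "THE FOLLOWING QUESTIONS ARE ABOUT HOW YOU HAVE BEEN FEELING AND HOW THINGS HAVE BEEN GOING FOR YOU OVER THE LAST 4 WEEKS", and ends at item 32 ("During the last 4 weeks, how often has physical health or emotional problems made it difficult for you to carry out social activities").
- The physical functioning items (3-12) ask about present health instead, for example "Does your current health limit your ability to". The general health items (1 and 33-36) have no four-week window. Item 2 compares with a year ago.

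The timing comes from three places in the protocol.

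- *Definition of the study*: patients are recruited after surgery, "with a deadline of 7 days after the operation for inclusion in the study".
- *Data collection*: physiotherapy starts "Once the period of 7 days has elapsed after the operation", provided there are no complications and no pleural drainage. No upper limit is given.
- *Work plan*: consent is Step 3, the first measurement is Step 4 ("Quality of Life Measure. SF-36" is on its list), and the programme starts at Step 5. All measures are repeated midway and at completion. Programme length is left as x days.

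No preoperative SF-36 and no short-recall version is mentioned. *Statistical analysis* calls for repeated-measures ANOVA for more than two related means, t-tests for related or independent means, and multiple regression. It ties none of these to the SF-36. Objective two is to show that better respiratory capacity improves quality of life.

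**The concern.** A form completed a week after an operation would naturally be taken as the postoperative starting point, with later forms showing recovery from it. With a 28-day window it is not that. Most of the days the patient is asked about came before the operation.

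Objective two is where this matters most. Spirometry at Step 4 describes the patient on that day. The protocol's own background (*Modification of respiratory mechanics*) puts the average postoperative fall in forced spirometric values at 40-50%, with return to preoperative values in 1-2 weeks. The vitality and mental health scores taken at the same step refer mainly to life before that fall. Change in one is therefore not the counterpart of change in the other. A paired t-test or a repeated-measures time effect starting from the first form would carry the same confusion.

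**Working it through.** **Items affected.** The Annex 1 table gives 10 + 4 + 2 + 5 + 4 + 2 + 3 + 5 items for the eight dimensions, plus 1 transition item, which is 36 as the protocol states. Items were assigned to dimensions by their wording and these counts.

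| Dimension | Items | Number | Four-week window |
|---|---|---|---|
| Role physical | 13-16 | 4 | yes |
| Role emotional | 17-19 | 3 | yes |
| Social function | 20, 32 | 2 | yes |
| Bodily pain | 21, 22 | 2 | yes |
| Vitality | 23, 27, 29, 31 | 4 | yes |
| Mental health | 24, 25, 26, 28, 30 | 5 | yes |
| Physical functioning | 3-12 | 10 | no |
| General health | 1, 33-36 | 5 | no |
| Transition item | 2 | 1 | no |

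With the window: 4 + 3 + 2 + 2 + 4 + 5 = 20 items in six dimensions. Without it: 10 + 5 + 1 = 16. Together 36.

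By response type, the 20 items divide into 7 yes/no (13-19), 3 extent or severity (20-22) and 10 time-frequency (23-32).

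**Preoperative share of the first form.** For a form on day s after surgery the share is (28 - s)/28. Only a value near day 7 is inferred from the protocol; the others are assumptions to show the range.

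- s = 5: 23/28 = 82%
- s = 7: 21/28 = 75%
- s = 10: 18/28 = 64%

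These are shares of calendar days, not of the score.

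**What this does to change from the first form.** As an illustration, assume a time-frequency answer averages over the days recalled. Let A be the preoperative level, B the level in the first postoperative week and C the level over a later window lying wholly after treatment began.

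- First form at day 7: 0.75A + 0.25B
- Observed change: C - 0.75A - 0.25B = 0.25(C - B) + 0.75(C - A)
- Recovery actually sought: C - B

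A patient who returns exactly to the preoperative level (C = A) shows 0.25(A - B), a quarter of the true recovery. If B is below A, a patient who regains three quarters of the loss (C = 0.75A + 0.25B) shows no change at all. Real answers may weight recent days more heavily, so this shows the mechanism and does not estimate its size.

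**Items 13-22.** One bad postoperative day is enough for a yes on the role items, and severe pain in the operative week may decide the extent and severity items. Day-averaging is not a safe model here, so the direction is left open.

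**End form.** With x days from the first session to the end form, the pre-treatment share is max(0, 28 - x)/28. For assumed x: 14 gives 14/28 = 50%, 21 gives 7/28 = 25%, and 28 or more gives 0%. Since x is not stated, the protocol does not settle which applies.

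**The case against.** The strongest reply is that this is a randomised comparison and the first form has the same window in both arms. In a two-arm repeated-measures analysis the treatment question is the group-by-time term, which the shared baseline window does not bias. A comparison of end forms alone does not use the baseline. The time effect that remains is uncontrolled in any case and already includes natural recovery. The analysis section is a general menu, and a statistical analysis plan that is not shown may choose well from it.

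Most of this stands. The arm comparison is not at issue, no specific SF-36 analysis is prescribed, and objective two can be examined across patients at the end form without any baseline. It is also true that day 7 is inferred and that bodily pain, the dimension closest to TENS, is among the items with uncertain direction.

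The reply does not remove the narrower problem. The protocol itself fixes the recall form and the timing of the first measurement, and no later plan can change what patients were asked. It describes a longitudinal study with three forms, offers related-means tests, and states an objective about improvement. A change score from the first form is the obvious analysis of that objective, and for items 23-32 it would not mean what it appears to mean.

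**Conclusion.** The point holds for within-patient change from the first form. At about day 7, roughly 75% of the recalled calendar days are preoperative (82% at day 5, 64% at day 10). The effect is clear for the ten time-frequency items: all of vitality, all of mental health and one of the two social-function items. It is of uncertain direction for items 13-22 and absent for physical functioning and general health. If the programme is shorter than 28 days, the end form also recalls pre-treatment days in both arms, which could dilute a difference between arms. The size is unknown because x is not given, and no loss of power is claimed.

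A reader might infer more than this. Three stronger readings are not supported.

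- *The TENS-versus-control comparison of quality of life is biased.* The first form precedes treatment and follows the same schedule in both arms, so its content is balanced on average.
- *Six dimensions are distorted by 75%.* The figure counts days and carries over to scores, at best, only for time-frequency items.
- *End-form windows differ between arms.* That requires programme length to differ. Objective three and the counting of treatment days suggest it may, while *Physiotherapeutic treatment* says the respiratory physiotherapy follows the same pattern. It remains conditional.

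The conclusion rests on the first form being completed close to day 7, which follows from the order of steps and is not a stated date. The change is worth making because it concerns a stated objective and costs little.

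**What to change.** Add the following to *Statistical analysis*:

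1. Compare the SF-36 dimensions between arms on the post-treatment form, with the first form as covariate and surgical group in the model. The first form is a legitimate covariate whatever window it covers, because it precedes treatment.
2. Do not interpret a paired t-test or a repeated-measures time effect starting from the first form as recovery in the six four-week dimensions.
3. For objective two, analyse change in physical functioning and general health alongside change in spirometry. Relate the four-week dimensions to spirometry across patients at the end form, without change from baseline. They stay within the objective.

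This needs a few sentences and no new data. The price is that the four-week dimensions contribute cross-sectional evidence to objective two instead of change.

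Optionally, if data collection is still open, give both arms one further self-completed SF-36 on the same fixed day, at least 28 days after the first session. Its window then holds no pre-treatment day. The cost is up to 180 forms (6 subgroups of 30), some non-return and, for programmes under 28 days, a window that includes days after treatment ended. The work plan dates recruitment 2015 to 2017 in a protocol dated 2021, so this may come too late; items 1 to 3 do not depend on it. The questionnaire items should not be reworded.

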Annex 2. Gill's Pain Questionnaire

[figure not shown]
McGill Pain Questionnaire

Patient's Name _____ Date _____ Time _____ AM/PM

PRI: S _____ A _____ E _____ M _____ PRI(T) _____ PPI _____

(1-10) (11-15) (16) (17-20) (1-20)

1 FLICKERING	11 TIRING	BRIEF MOMENTARY TRANSIENT	RHYTHMIC PERIODIC INTERMITTENT	CONTINUOUS STEADY CONSTANT
QUIVERING	EXHAUSTING			
PULSING	12 SICKENING			
THROBBING	SUFFOCATING			
BEATING	13 FEARFUL			
POUNDING	FRIGHTFUL			
2 JUMPING	TERRIFYING			
FLASHING	14 PUNISHING			
SHOOTING	GRUELLING			
3 PRICKING	CRUEL			
BORING	VICIOUS			
DRILLING	KILLING			
STABBING	15 WRETCHED			
LANCINATING	BLINDING			
4 SHARP	16 ANNOYING			
CUTTING	TRoublesome			
LACERATING	MISERABLE			
5 PINCHING	INTENSE			
PRESSING	UNBEARABLE			
GNAWING	17 SPREADING			
CRAMPING	RADIATING			
CRUSHING	PENETRATING			
6 TUGGING	PIERCING			
PULLING	18 TIGHT			
WRENCHING	NUMB			
7 HOT	DRAWING			
BURNING	SQUEEZING			
SCALDING	TEARING			
SEARING	19 COOL			
8 TINGLING	COLD			
ITCHY	FREEZING			
SMARTING	20 NAGGING			
STINGING	NAUSEATING			
9 DULL	AGONIZING			
SORE	DREADFUL			
HURTING	TORTURING			
ACHING	PPI			
HEAVY	0 NO PAIN			
10 TENDER	1 MILD			
TAUT	2 DISCOMFORTING			
RASPING	3 DISTRESSING			
SPLITTING	4 HORRIBLE			
